8.3.3.3. GP5 Question From FACT-G

FACT-G includes a question referred to as GP5 which asks, "I am bothered by side effects of treatment". The answer is provided by the patient who selects one of the following five choices: Not at all (0), A little bit (1), Some-what (2), Quite a bit (3), or Very much (4). GP5 scores will be descriptively summarized at baseline, each post-baseline time point, and the last on-treatment assessment.

8.3.3.4. EQ-VAS

EQ-VAS is the sixth item of EQ-5D-5L. It records the patient's self-rated health on a vertical visual analogue scale with endpoints labeled "the best health you can imagine" and "the worst health you can imagine." A patient is asked to "mark an X on the scale to indicate how your health is TODAY" and "write the number you marked on the scale in the box below."

EQ-VAS at each post-baseline time point, and the last on-treatment assessment, and change in scores from baseline will be summarized using descriptive statistics. The change in EQ-VAS from baseline at specific timepoints (3 and 6 months) will be compared between the two arms. The EQ-VAS at 3 months will be calculated as the average of its score on C2D29 visit and C3D1 visit; similarly, the EQ-VAS at 6 months will be calculated as the average of its score on C5D29 visit and C6D1 visit.

8.3.4. Disease Control Rate

Disease control will be defined as having a BOR of confirmed CR, or confirmed PR, or BOR of SD lasting for 3 months or longer. Disease control rate (DCR) will be calculated as the proportion of patients with disease control. DCR will be also calculated at 6, 9, and 12 months.

CONFIDENTIAL Page 20 of 29

Disease control rate based on IRR and INV will be summarized in the Ex11 ITT Population and AP ITT Population.

8.3.5. Time to Tumor Progression

TTP is defined as the interval between the date of randomization and the earliest documented evidence of disease progression.

Censoring rules for TTP will be same as those specified for PFS in Section 8.1.1. Additionally, patients who died without documented progression will be censored at the latest date of evaluable progression-free tumor assessment.

TTP (months) = [date of event or censoring – date of randomization +1]/30.4375 TTP will be analyzed in a similar fashion as PFS.

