time to tumor progression (TTP) in patients receiving SUTENT plus best supportive care versus patients receiving placebo plus best supportive care. Other objectives included PFS, ORR, and overall survival (OS). Patients were randomized (2:1) to receive either 50 mg SUTENT or placebo orally, QD, on Schedule 4/2 until disease progression or withdrawal from the study for another reason. Treatment was unblinded at the time of disease progression. Patients randomized to placebo were then offered crossover to open-label SUTENT and patients randomized to SUTENT were permitted to continue treatment per investigator judgment. In the double-blinded treatment phase, median TTP was 27.3 weeks in the SUTENT group and 6.4 weeks in the placebo group. Median PFS was 24.1 weeks in the SUTENT group and 6.0 weeks in the placebo group.

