#### 9.8.5.2.6. Time to Tumor Progression

The secondary endpoint of TTP is defined as the interval between the date of randomization and the earliest documented evidence of disease progression based on the independent radiologic review. Patients who undergo surgical resection of target or non-target lesions, who have received other anticancer treatments for GIST, who do not have a documented date of progression or death due to any cause, or who die prior to tumor progression will be censored at

the date of the last assessment. TTP will be analyzed using similar model as PFS for both Ex 11 ITT and AP ITT separately.

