3.6. General Analysis Conventions

Continuous data will be summarized using descriptive statistics (number of patients with assessment, mean, median, standard deviation, minimum, and maximum). Categorical data will be summarized using frequencies and proportions. Time-to-event data will be reported in months, and summarized via Kaplan-Meier (KM) methodology using the 25th, 50th (median), and 75th percentiles with associated 2-sided 95% confidence intervals (CIs), and time point survival probabilities with associated 2-sided 95% CIs.

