8. EFFICACY ANALYSIS

8.1. Primary Endpoint

8.1.1. Primary Analysis

The primary endpoint of PFS based on IRR is defined as the time interval between the date of randomization and the earliest documented evidence of the first disease progression based on IRR or death due to any cause, whichever occurs first.

Special rules of defining an event or censoring PFS are as follows:

- For patients who do not have adequate tumor assessment at baseline (adequate baseline is defined as having baseline assessment ≤31 days before the date of first dose or date of randomization if the patient did not receive study treatment) or do not have any adequate post-baseline assessments (defined as non-missing and evalulable assessment), PFS will be censored at randomization date (PFS=1 day) unless they die ≤14 weeks from the date of randomization, they will be considered to have a PFS event at death date.
- For patients who received a new anticancer therapy (including surgical resection on GIST lesions, radiotherapy of GIST lesions, or an anticancer treatment other than the study treatment) before event, PFS will be censored at the date of the latest evaluable progression-free tumor assessment prior to the start of new anticancer therapy. If date of progression occurs on the same date of as the start of new anti-cancer therapy, the progression will be counted as an event.
- For patients who did not have disease progression and did not die, PFS will be censored at the time of the latest date of evaluable progression-free tumor assessment.
- For patients who have first disease progression or die after two or more consecutive missed/non-evaluable assessments since the last evaluable tumor assessment, PFS will be censored at the time of the last evaluable progression-free tumor assessment.

CONFIDENTIAL Page 15 of 29

PFS (months) = [(date of event or censoring - date of randomization) +1]/30.4375

The primary endpoint PFS will be analyzed in both Ex11 ITT Population and AP ITT Population.

Analysis for PFS in Ex11 ITT population will be stratified by intolerance to imatinib per IRT [yes vs. no]. Analysis for PFS in AP ITT population will be stratified by the randomization stratification factors per IRT (mutation status [KIT exon 9 vs. KIT exon 11 vs. KIT/PDGFRA WT vs. other KIT {absence of exon 9 or 11}/PDGFRA] and intolerance to imatinib [yes vs. no]).

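### Time to tumour progression censors deaths and is summarised by Kaplan-Meier, which overstates the proportion of patients who progress; a cumulative incidence should be added

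*SAP*

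**What the plan says.** SAP 8.3.5 defines the endpoint by progression alone: "TTP is defined as the interval between the date of randomization and the earliest documented evidence of disease progression". On censoring it first imports the primary endpoint's rules, "Censoring rules for TTP will be same as those specified for PFS in Section 8.1.1", and then adds "Additionally, patients who died without documented progression will be censored at the latest date of evaluable progression-free tumor assessment". On method it says "TTP will be analyzed in a similar fashion as PFS". Through SAP 8.1.1 and 3.6 this means a stratified log-rank test, a stratified Cox model, and times "summarized via Kaplan-Meier (KM) methodology using the 25th, 50th (median), and 75th percentiles", together with time-point probabilities and, as for PFS, a KM plot. No time points are named for TTP.

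Protocol 9.8.5.2.6 handles deaths in the same way: patients "who die prior to tumor progression will be censored at" their last assessment. Neither document plans a cumulative incidence or names death as a competing event.

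One imported PFS rule concerns patients without an adequate baseline or post-baseline scan. SAP 8.1.1 censors them at randomization (day 1) "unless they die ≤14 weeks from the date of randomization, they will be considered to have a PFS event at death date".

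TTP is listed among the other secondary endpoints. SAP 8.3 analyses it in both the Ex11 and AP ITT populations, by independent review and by investigator, and SAP 8.3.7 repeats the independent-review analysis under Choi criteria. It is not among the six tests in SAP 8.5.

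**The concern.** Kaplan-Meier with deaths censored treats a patient who died as someone who could still progress later. 1-KM then describes a hypothetical population in which nobody dies before progressing. It does not estimate the proportion of randomized patients whose tumour progresses, yet readers will usually take a TTP curve and its time-point probabilities in that sense. The bias runs in one direction, upwards, and grows with follow-up and with the share of PFS events that are deaths.

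There is also a small gap in the rules. The imported 14-week clause is worded as an event rule, while the TTP section censors every death without progression at the last progression-free scan. A patient who dies early without any post-baseline scan has no such date after randomization.

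At stake is the descriptive reading of a secondary endpoint, not a formal test.

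**Working it through.** **Inputs.** Median PFS 6 months (sunitinib) and 9 months (ripretinib), 213 patients per arm, 21 months' accrual plus 8 months' follow-up, 20% dropout (SAP 2.3). The earlier sunitinib trial: "median TTP was 27.3 weeks in the SUTENT group and 6.4 weeks in the placebo group", with median PFS 24.1 weeks on sunitinib (Protocol 1.4). Median OS 40 and 53.3 months (SAP 2.3).

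**The plan's own figure.** For HR 0.667, two-sided 0.05 and 90% power, Freedman's formula gives (1.960 + 1.282)² × (1.667/0.333)² ≈ 263 events, against the stated 262. Schoenfeld's gives 256, and 90.7% power at 262 events. The stated inputs are therefore reproduced. The plan gives no figure for TTP.

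**Share of PFS events that are deaths, f.** The documents do not state it. If PFS and TTP in the earlier trial were both exponential, the progression hazard divided by the PFS hazard is 24.1/27.3 = 0.883, so f = 0.117. A rough ceiling is the OS hazard over the PFS hazard: 6/40 = 15% for sunitinib and 9/53.3 = 17% for ripretinib. I use 3-15% as the range.

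**Formulas.** With PFS hazard h = ln 2/median:

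- 1-KM(t) = 1 − exp(−(1−f)ht)
- cumulative incidence(t) = (1−f)(1 − exp(−ht))

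The standard error of 1-KM is Greenwood's for n = 213, with uniform accrual and dropout taken as 20% per year. That reading of the 20% is an assumption.

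**Results at 12 months** (excess computed before rounding):

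| f | Sunitinib 1-KM | Cum. inc. | Excess, points (SE) | Ripretinib 1-KM | Cum. inc. | Excess, points (SE) |
|---|---|---|---|---|---|---|
| 3% | 73.9% | 72.8% | 1.2 (0.35) | 59.2% | 58.5% | 0.7 (0.19) |
| 5% | 73.2% | 71.2% | 2.0 (0.57) | 58.4% | 57.3% | 1.1 (0.30) |
| 10% | 71.3% | 67.5% | 3.8 (1.06) | 56.5% | 54.3% | 2.2 (0.57) |
| 11.7% | 70.6% | 66.2% | 4.4 (1.21) | 55.8% | 53.2% | 2.5 (0.66) |
| 15% | 69.2% | 63.8% | 5.5 (1.47) | 54.4% | 51.3% | 3.1 (0.81) |

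For example, sunitinib at 11.7%: ht = 1.386; 1 − exp(−0.883 × 1.386) = 0.706; 0.883 × 0.75 = 0.662. A simulation with scans every 6 weeks to week 36 and every 12 weeks after that, censoring deaths at the last scan, gives 1.24 and 0.69 SE at 11.7%.

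**Other time points, f = 11.7%.** At 6 months the excess is 0.45 SE (sunitinib) and 0.25 SE (ripretinib). At 18 months it is 6.8 and 4.4 points.

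**Between arms at 12 months.** With 11.7% in both arms, the difference is 70.6 − 55.8 = 14.8 points by KM and 66.2 − 53.2 = 13.0 by cumulative incidence. The shift is about 1.8 points, or 0.35 SE of the difference. With ripretinib at its 17% ceiling and sunitinib at 11.7%, the excesses are 3.5 and 4.4 points, so the shift falls to about 0.9.

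**Early deaths.** The main group the 14-week clause could reach is patients who die before the first 6-week scan. Their expected number per arm is 213 × f × (1 − exp(−h × 42/30.4375)). At 11.7% this is 3.7 (sunitinib) and 2.5 (ripretinib); at 5% it is 1.6 and 1.1. In the simulation at 11.7%, counting them as TTP events raises the 12-month excess from 4.7 to 5.3 points (sunitinib) and from 2.7 to 3.2 (ripretinib).

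**The case against.** Censoring deaths is the usual definition of TTP, and the SAP nowhere claims that 1-KM estimates the proportion of patients who progress. The log-rank test and Cox hazard ratio remain valid as cause-specific comparisons, and TTP lies outside the testing hierarchy. All of this stands, and it limits the point to the probability summary.

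The size is also uncertain. The 11.7% comes from two medians in one arm of an earlier trial. It assumes exponential times and the same censoring rules for both endpoints, ignores sampling error, and carries over to a different drug. The SAP names no 12-month time point for TTP, although 12 months is a planned time point for disease control rate (SAP 8.3.4). A reader might take 0.7 to 1.2 SE as the established bias. The documents support only a conditional range.

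A reader might also infer that the SAP turns some early deaths into TTP events. It does not. The definition counts only progression, the added sentence in 8.3.5 censors all deaths without progression, the 14-week clause speaks of a PFS event, and the protocol also censors such deaths. Nor do the documents establish zero or negative TTP values. SAP 8.1.1 already places patients without a post-baseline scan at day 1, and a non-positive time arises only if the baseline scan is taken as the last progression-free assessment.

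Finally, a claim that the method inflates the treatment difference rests on equal death shares in the two arms, and even then the shift is small.

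**Conclusion.** The point holds for the Kaplan-Meier summary. As written, TTP probabilities, percentiles and curves will overstate how many patients progress, and how soon, whenever deaths precede progression. Over an assumed death share of 3-15%, with exponential times and the plan's medians, the 12-month excess is about 0.2 to 1.5 SE per arm. At 11.7% it is about 4.4 points for sunitinib and 2.5 for ripretinib. At that share in both arms the between-arm difference moves by about 1.8 points (0.35 SE), and by less if ripretinib has the larger death share.

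On early deaths, what remains is an overlap between the imported 14-week clause and the TTP sentence, and an unclear censoring date for a few patients per arm. The text favours censoring.

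This is a cheap improvement to a descriptive secondary analysis. No confirmatory conclusion is affected.

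**What to change.** In SAP 8.3.5:

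1. Add the Aalen-Johansen cumulative incidence of progression, with death as a competing event, as the probability summary: estimates at named time points, 95% confidence intervals and a plot.
2. Keep the KM median alongside it for comparison with earlier trials.
3. Label the stratified log-rank test and the hazard ratio as cause-specific.
4. As a minor clarification, state that the 14-week early-death event clause of 8.1.1 does not apply to TTP, and that patients who die with no evaluable post-baseline scan are censored at randomization (day 1) in the cause-specific and KM analyses.

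The cost is SAP wording and one extra standard analysis on data already collected. The drawback is that the headline TTP probability becomes less directly comparable with older KM-based reports; item 2 eases this.

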8.3.6. PFS Based on Investigator Assessment

As a sensitivity analysis to the primary efficacy analysis, PFS based on Investigator assessment (INV) is defined as the interval between the date of randomization and the earliest documented evidence of disease progression based on INV or death due to any cause, whichever occurs first. Special rules for defining a PFS event or censoring PFS based on Investigator assessment will be similar to those specified for the primary endpoint PFS in Section 8.1.

PFS based on INV will be analyzed in an analogous fashion to PFS based on IRR. As noted in Section 8.1, the following analyses will be performed based on the Investigator assessment and used as sensitivity analyses for the primary endpoint PFS based on IRR:

- PFS based on INV using mRECIST criteria in Ex11 ITT population
- PFS based on INV using mRECIST criteria in AP ITT population

In addition to the sensitivity analyses based on the investigator assessment, the discordance between the IRR and INV will be summarized.

8.3.7. Efficacy Based on Choi Criteria by Independent Radiologic Review

The analyses of the endpoints PFS, ORR, and TTP based on IRR will be repeated using the tumor assessments per Choi criteria among patients evaluable for Choi (CT scan present at least partially at baseline assessment and at at least one post-baseline assessment).

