### 9.2.2.2. Other Secondary Endpoints

- QOL as measured by using EORTC QLQ-C30, DLQI, and the GP5 question from FACT-G
- TTP
- Disease control rate (DCR; CR + PR + SD) at 6, 9 and 12 months, based on independent radiologic review
- PFS based on investigator assessment
- Efficacy using Choi criteria based on independent radiologic review

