#### 9.8.5.2.9. *Efficacy Based on Choi Criteria Based on Independent Radiologic Review*

The primary PFS, ORR, TTP, and DCR analyses will be repeated using the Choi criteria in place of mRECIST for both Ex 11 ITT and AP ITT separately.

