4. ANALYSIS POPULATIONS

4.1. Intent to Treat Population

The KIT Exon 11 ITT (Ex11 ITT) Population is defined as all randomized patients who are designated as having a mutation in KIT Exon 11 per IRT. Patients in this population will be analyzed according to the treatment which they were scheduled to receive.

CONFIDENTIAL Page 11 of 29

The all patients (AP) ITT Population is defined as all patients who are randomized. Patients in this population will be analyzed according to the treatment which they were scheduled to receive.

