8.2.1. Objective Response Rate

Best overall response (BOR) will be assessed based on reported overall tumor responses at different evaluation timepoints from the date of randomization until the first documentation of

CONFIDENTIAL Page 16 of 29

disease progression, death, surgical resection on GIST lesions or radiotherapy of GIST lesions, or start of new anticancer therapy, whichever occurs first.

BOR Based on Confirmed Responses:

- Confirmed Complete Response (CR): at least two determinations of CR at least 4 weeks apart (allowing a minus 3-day window) and before first documentation of disease progression
- Confirmed Partial Response (PR): at least two determinations of PR or better (PR followed by PR or PR followed by CR) at least 4 weeks apart (allowing a minus 3-day window) and before first documentation of disease progression (and not qualifying for a CR)
- Stable Disease (SD): at least one SD assessment (or better) ≥ 6 weeks (allowing a minus 3-day window) after the date of randomization and before first documentation of PD (and not qualifying for confirmed CR or confirmed PR).
 - Non-CR/non-PD per IRR review will be reported together as SD (applicable only to patients without target lesions at baseline per IRR): at least one non-CR/non-PD assessment (or better) ≥ 6 weeks (allowing a minus 3-day window) after the date of randomization and before first documentation of PD (and not qualifying for confirmed CR or confirmed PR).
- Progressive Disease (PD): first documentation of PD ≤ 14 weeks after the date of randomization (and not qualifying for confirmed CR, confirmed PR, or SD).
- Not evaluable (NE): all other cases.
 - Undefined per IRR review will be reported together as NE (applicable only to patients with neither target lesions nor non-target lesions at baseline per IRR)

Objective response is defined as BOR of either a confirmed CR or a confirmed PR. ORR is defined as the proportion of patients with a confirmed CR or a confirmed PR as the BOR. Patients with non-evaluable or missing response will be treated as non-responders and will be included in the denominator during calculation.

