8.3. Analysis of Other Secondary Efficacy Endpoints

All other secondary efficacy endpoints will be analyzed for Ex11 ITT and AP ITT populations. The secondary endpoints of DOR, TTR, TTP will be analyzed based on both IRR and INV. PFS based on INV will be analyzed as other secondary efficacy endpoints.

CONFIDENTIAL Page 18 of 29

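### The Choi analysis set in SAP 8.3.7 requires a post-baseline CT, which inflates Choi ORR and removes some early deaths from Choi PFS

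*SAP*

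**What the plan says.** Choi efficacy by independent review is an other secondary endpoint (Protocol 9.2.2.2; SAP 2.1.3). SAP 8.3.7 states: "The analyses of the endpoints PFS, ORR, and TTP based on IRR will be repeated using the tumor assessments per Choi criteria", and restricts this to patients "among patients evaluable for Choi (CT scan present at least partially at baseline assessment and at at least one post-baseline assessment").

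The parent section, SAP 8.3, says: "All other secondary efficacy endpoints will be analyzed for Ex11 ITT and AP ITT populations". ITT carries no imaging condition: "The all patients (AP) ITT Population is defined as all patients who are randomized" (SAP 4.1), and Ex11 ITT is the subset designated KIT exon 11 in the randomization system.

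The analyses being repeated already cover patients without post-baseline scans:

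- **ORR (SAP 8.2.1):** "Patients with non-evaluable or missing response will be treated as non-responders and will be included in the denominator during calculation".
- **PFS (SAP 8.1.1):** a patient with no adequate post-baseline assessment is censored at day 1, unless death occurs within 14 weeks of randomization, which is an event.
- **TTP (SAP 8.3.5):** the PFS censoring rules apply, and death without documented progression is also censored.

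SAP 8.3.7 gives no reason for the restriction and does not mark it as an exception to 8.3.

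**The concern.** The two halves of the Choi condition differ in kind. A baseline CT is fixed before treatment starts. A post-baseline CT exists only if the patient lives and stays in the study long enough to be scanned, and the first scheduled scan is at Cycle 2 Day 1, about 6 weeks in (Protocol Table 1, footnote 22). The trial is open-label, so early withdrawal or failure to start treatment may differ between arms, and early deaths may too. The arms of the Choi set are then no longer the randomized arms.

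At stake is the reading of Choi against mRECIST. If both the criteria and the population change, a reader cannot tell which produced a difference. Choi ORR would look higher than ORR calculated with the SAP's own denominator, and an early-mortality difference in either direction could disappear from Choi PFS.

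**Working it through.** The plan gives no Choi sample size, evaluable share or expected response rate, so there is no stated figure to reproduce. The check takes the endpoints one at a time.

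**Inputs**

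- 213 patients per arm (SAP 2.3).
- ORR of 24%, for illustration only. This is the Phase 1 rate in second- and third-line patients by investigator RECIST 1.1 (Protocol 1.3.2.3 and 1.5.1), not a Choi rate by independent review.
- q, the share of an arm with no post-baseline CT: not in the documents; assumed 2% to 10%.
- Early death shares of 2% and 6%: assumed.

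**ORR.** A confirmed response needs two determinations at least 4 weeks apart (SAP 8.2.1), so a patient with no post-baseline CT cannot be a Choi responder. The restriction leaves the numerator alone and shrinks the denominator:

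ORR in the evaluable set = ORR in ITT / (1 - q)

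| q | Calculation | Reads as |
|---|---|---|
| 2% | 0.24 / 0.98 | 24.5% |
| 5% | 0.24 / 0.95 | 25.3% |
| 10% | 0.24 / 0.90 | 26.7% |

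If both arms truly have 24% and q is 5% in one and 10% in the other, the artefact is 26.7 - 25.3 = 1.4 points. With 2% and 8% it is 26.1 - 24.5 = 1.6 points. For scale, the standard error of the difference is the square root of 2 × 0.24 × 0.76 / 213 = 0.041, or 4.1 points, so 1.4 points is about a third of one standard error.

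**PFS.** There are two groups without a post-baseline CT.

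- Those not known to have died within 14 weeks are censored at day 1 under 8.1.1. They are in no later risk set, so removing them does not move the log-rank test or the hazard ratio.
- Those who die within 14 weeks are events under 8.1.1. The restriction removes them. At 2% and 6% of 213, that is about 4 and 13 deaths.

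A simulation shows the size: 213 per arm, 1,000 replicates, no treatment effect on later progression, 6-month median after the first scan in both arms, 4% scan-less dropouts per arm, and an unstratified log-rank observed/expected hazard ratio (experimental to control).

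| Early deaths, control / experimental | PFS HR, ITT rules | PFS HR, evaluable set | TTP HR, ITT and evaluable |
|---|---|---|---|
| 2% / 2% | 1.001 | 1.001 | 1.001 and 1.001 |
| 2% / 6% | 1.051 | 0.999 | 0.999 and 0.999 |
| 6% / 2% | 0.951 | 1.002 | 1.002 and 1.002 |

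The restriction erases a shift of about 0.05 in the hazard ratio, whichever arm has more early deaths.

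**TTP.** Early deaths and early dropouts without a post-baseline scan are all censored at day 1 under ITT rules. Removing them changes nothing, as the last column shows.

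**The case against.** The best defence is that SAP 8.3 is a general lead-in and 8.3.7 a specific rule beneath it. Other endpoints under that lead-in also use subsets: duration of response and time to response cover confirmed responders only. On this reading the Choi-evaluable subset is simply taken within each of Ex11 ITT and AP ITT. That softens the conflict with 8.3 but does not remove it: those two endpoints are limited to responders by definition, whereas PFS and ORR are defined for every randomized patient. Nor does it answer the selection problem, which exists however 8.3 is read.

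Several stronger readings are tempting, and the documents do not support them.

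- **The SAP contradicts the protocol.** Protocol 9.8.5.2.9 does say the analyses "will be repeated using the Choi criteria in place of mRECIST for both Ex 11 ITT and AP ITT separately". But SAP Section 1 says the SAP may modify the protocol's plans and supersedes its statistical sections. The difference may be intended and is not an error in itself.
- **Every death in the first 6 weeks is lost.** Any post-baseline CT qualifies. Imaging may be done up to 7 days before the visit, unscheduled assessments are allowed, an end-of-treatment scan is scheduled with stated exceptions, and a scan is required before stopping for clinical deterioration (Protocol Table 1 footnotes; 6.10.1). Some early deaths stay in the set.
- **Dropouts in general bias Choi PFS and TTP.** Only patients who leave before any post-baseline CT are removed, and those not counted as early deaths would be censored at day 1 anyway.
- **A trial conclusion is at risk.** Choi is not in the hierarchy of SAP 8.5, and the mRECIST results are still reported in full ITT.

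One practical objection has some weight. MRI is permitted, and technique may change for a safety risk. Without the post-baseline condition, a patient with a baseline CT and only MRI afterwards counts as a Choi non-responder, which turns a modality limit into a treatment failure. Because the same technique must otherwise be kept throughout, such patients should be few, and they can be counted and shown.

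**Conclusion.** The point holds for two results, Choi ORR and Choi PFS. The post-baseline CT condition disables the non-responder rule of SAP 8.2.1 and the 14-week death rule of SAP 8.1.1 for exactly the patients those rules were written for, and SAP 8.3.7 gives no reason for it.

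The likely effect is small: roughly half a point to under three points on an arm's ORR, about 1.5 points on the difference if the missing shares are unequal, and about 0.05 on the PFS hazard ratio if early deaths differ by 4 percentage points. These sizes rest on assumed missing and early-death shares and on a borrowed 24% response rate; the documents give none of these for Choi. The direction for ORR within an arm is certain whenever q is above zero. The direction for the treatment comparison depends on which arm loses more patients.

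TTP is essentially unaffected, as are the primary analysis and the familywise error rate. This is a low-cost improvement to a secondary analysis.

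**What to change.** Replace the population clause in SAP 8.3.7 so that:

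1. The Choi set is all Ex11 ITT and AP ITT patients with at least a partial CT at baseline.
2. For ORR, patients without an evaluable post-baseline Choi assessment count as non-responders, as in 8.2.1.
3. For PFS, the 8.1.1 rules apply, including deaths within 14 weeks as events. TTP follows 8.3.5.
4. The current evaluable set is kept as a labelled supportive analysis.
5. The number of patients without a post-baseline CT is reported by arm with reasons (death, withdrawal, MRI only, other), so that MRI-only patients can be seen separately.

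The cost is a sentence or two in the SAP and one extra table. No new data are needed and the sample size does not change. Choi ORR will be slightly lower, and the few baseline-CT patients later imaged only by MRI will count as non-responders in the main Choi analysis.
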